4.2 Treatment Dosage and Administration

4.2.1 Preparation and Administration of Avelumab

Specific instructions for the preparation infusion fluid and administration of infusion solution are provided in the Pharmacy Manual.

Avelumab is administered on an outpatient basis. Avelumab 10mg/kg body weight, diluted with 0.45% or 0.9% saline solution, will be administered as a 60 minute intravenous (IV) infusion every 2 weeks.

4.2.2 Monitoring of Dose Administration

Patients will be monitored during and after the infusion with assessment of vital signs at the times specified in the Schedule of Events.

Patients will be monitored for the presence of infusion-related reactions. Dose modification and toxicity management for infusion-related reactions are outlined in the dose modification section (Section 4.3).

As with any antibody, allergic reactions to dose administration are possible. Appropriate drugs and medical equipment to treat acute anaphylactic reactions must be immediately available, and study personnel must be trained to recognize and treat anaphylaxis. The study site must have immediate access to emergency resuscitation teams and equipment in addition to the ability to admit subjects to an intensive care unit if necessary.

4.2.3 Criteria for Starting Subsequent Cycles

A cycle may be repeated every 28 days if the patient is without ongoing Grade 3 nonhematologic or Grade 4 hematologic toxicities attributable to study treatment.

4.3 Toxicities and Dosing Delays/Dose Modifications

Any patient who receives treatment on this protocol will be evaluable for toxicity. Each patient will be assessed for the development of toxicity according to the NCI Common Toxicity Criteria for Adverse Events (CTCAE), version 4.03.

Adverse events (both non-serious and serious) associated with avelumab exposure may represent an immunologic etiology. These adverse events may occur shortly after the first dose or several months after the last dose of treatment. Avelumab must be withheld for drug-related toxicities and severe or life-threatening AEs as listed in Sections 4.3.1-4.3.3.

4.3.1 Management of Immune-Related Adverse Events

Gastrointestinal irAEs		
Severity of diarrhea/Colitis (NCI-CTCAE v4)	Management	Follow-up

Grade 1	Continue avalumate therapy	Close menitoring for worsening
Diarrhea: < 4 stools/day over	Continue avelumab therapy	Close monitoring for worsening symptoms
baseline;	Symptomatic treatment (e.g.	Symptoms
Colitis: asymptomatic	loperamide)	Educate subject to report worsening
		immediately
		,
		If worsens:
		Treat as Grade 2 or 3/4
Grade 2	Delay avelumab therapy	If improves to Grade 1:
Diarrhea: 4 to 6 stools per day over	Symptomatic treatment	Resume avelumab therapy
Baseline; i.v. fluids indicated < 24		
hours; not interfering with ADL		If persists > 5-7 days or recur:
Colitis: abdominal pain; blood in stool		0.5 to 1.0 mg/kg/day methylprednisolone or
Stool		equivalent
		equivalent
		When symptoms improve to Grade
		1, taper steroids over at least 1
		month, consider prophylactic
		antibiotics for opportunistic
		infections, and resume avelumab
		therapy per protocol.
		If worsens or persists > 3 to 5 days
		with oral
		steroids: Treat as Grade ³ / ₄
Grade 3 to 4	Discontinue avelumab therapy	If improves:
Diarrhea (Grade 3): \geq 7 stools per	per protocol	Continue steroids until Grade 1,
day over Baseline; incontinence; i.v.		then taper over at least 1 month
fluids ≥ 24 h; interfering with ADL	1.0 to 2.0 mg/kg/day	
	methlyprednisolone i.v. or	If persists > 3 to 5 days, or recur
Colitis (Grade 3): severe abdominal	equivalent	after improvement:
pain, medical intervention indicated,		Add infliximab 5mg/kg (if no
peritoneal signs	Add prophylactic antibiotics for	contraindication),
Grade 4: life-threatening, perforation	opportunistic infections Consider lower endoscopy	Note: infliximab should not be used in cases of perforation or sepsis
•	Consider lower endoscopy	In cases of perioration of sepsis
Dermatologic irAEs Grade of Rash	Management	F _U
(NCI-CTCAE v4)	Management	Follow-up
Grade 1 to 2	Symptomatic therapy (for	If persists > 1 to 2 weeks or recurs:
Covering $\leq 30\%$ body surface area	example, antihistamines, topical	Consider skin biopsy
 	steroids)	Delay avelumab therapy
	Continue avelumab therapy	Consider 0.5-1.0 mg/kg/day
		methylprednisolone i.v. or oral
		equivalent. Once improving, taper
		steroids over at least 1 month,
		consider prophylactic antibiotics for
		opportunistic infections, and resume
		avelumab therapy
		If worsens: Treat as Grade 3 to 4
Grade 3 to 4	Delay or discontinue avelumab	If improves to Grade 1:
Covering > 30% body surface area;	therapy	Taper steroids over at least 1 month
Life-threatening consequences		and add
	Consider skin biopsy	prophylactic antibiotics for
		opportunistic
	Dermatology consult	infections
		Resume avelumab therapy
	1.0 to 2.0 mg/kg/day	
	methylprednisolone i.v. or i.v.	
	equivalent	

Pulmonary irAEs		
Grade of Pneumonitis	Management	Follow-up
(NCI-CTCAE v4)		De images at least average 2 verales
Grade 1 Radiographic changes only	Consider delay of avelumab therapy Monitor for symptoms every 2 to 3 days	Re-image at least every 3 weeks If worsens: Treat as Grade 2 or Grade 3 to 4
	Consider Pulmonary and Infectious Disease consults	
Grade 2	Delay avelumab therapy	Re-image every 1 to 3 days
Mild to moderate new symptoms	Pulmonary and Infectious Disease consults	If improves: When symptoms return to near
	Monitor symptoms daily; consider hospitalization	baseline, trapper steroids over at least 1 month and then resume avelumab therapy and consider
	1.0 mg/kg/day methyl-prednisolone i.v. or oral equivalent	prophylactic antibiotics If not improving after 2 weeks or worsening: Treat as Grade 3 to 4
	Consider bronchoscopy, lung biopsy	
Grade 3 to 4	Discontinue avelumab therapy	If improves to Baseline:
Severe new symptoms; New/worsening hypoxia; Life-	Hospitalize	Taper steroids over at least 6 weeks
threatening	Pulmonary and Infectious Disease consults	If not improving after 48 hours or worsening: Add additional immunosuppression (for example, infliximab,
	2 to 4 mg/kg/day methylprednisolone i.v. or i.v. equivalent	cyclophosphamide, i.v. immunoglobulin, or mycophenolate mofetil)
	Add prophylactic antibiotics for opportunistic infections	
	Consider bronchoscopy, lung biopsy	
Hepatic irAEs		
Grade of Liver Test Elevation (NCI-CTCAE v4)	Management	Follow-up
Grade 1	Continue avelumab therapy	Continue liver function monitoring
Grade 1 AST or ALT > ULN to 3.0 x ULN and/or Total bilirubin > ULN to 1.5 x ULN		If worsens: Treat as Grade 2 or 3-4
Grade 2	Delay avelumab therapy	If returns to Baseline:
AST or ALT > 3.0 to \leq 5 x ULN and/or total bilirubin > 1.5 to \leq 3 x ULN	Increase frequency of monitoring to every 3 days	Resume routine monitoring, resume avelumab therapy
		If elevations persist > 5-7 days or
		worsen : 0.5 to 1 mg/kg/day
		methylprednisolone or oral
		equivalent and when LFT returns to Grade 1 or Baseline, taper steroids
		over at least 1 month, consider
		prophylactic antibiotics for opportunistic infections, and resume

		avelumab therapy	
Grade 3 to 4	Discontinue avelumab therapy	If returns to Grade 2:	
AST or ALT > 5 x ULN and/or total		Taper steroids over at least 1 month	
bilirubin $> 3 \times ULN$	Increase frequency of monitoring to	· · · · · · · · · · · · · · · · · · ·	
	every 1 to 2 days 1.0 to 2.0	If does not improve in > 3 to 5 days,	
	mg/kg/day methylprednisolone i.v.	worsens or rebounds:	
	or i.v. equivalent	Add mycophenolate mofetil 1 gram	
		(g) twice daily	
	Add prophylactic antibiotics for	(3)	
	opportunistic infections	If no response within an additional 3	
		to 5 days, consider other	
	Consult gastroenterologist	immunosuppressants per local	
	Contrait guoti contereregiet	quidelines	
	Consider obtaining MRI/CT scan of	9	
	liver and liver biopsy if clinically		
	warranted		
Endocrine irAEs		1	
Endocrine Disorder	Management	Follow-up	
Asymptomatic TSH abnormality	Continue avelumab therapy	•	
	If TSH < 0.5 x LLN, or TSH > 2 x ULN, or consistently out of range in 2		
	subsequent measurements: include T	subsequent measurements: include T4 at subsequent cycles as clinically	
	indicated; consider endocrinology cor		
Symptomatic endocrinopathy	Evaluate endocrine function	If improves (with or without	
		hormone replacement):	
	Consider pituitary scan	Taper steroids over at least 1 month	
		and consider prophylactic antibiotics	
	Symptomatic with abnormal	for opportunistic infections	
	lab/pituitary scan:		
	Delay avelumab therapy	Resume avelumab therapy	
	1 to 2 mg/kg/day		
	methylprednisolone i.v. or by mouth	Subjects with adrenal insufficiency	
	equivalent	may need to continue steroids with	
	Initiate appropriate hormone	mineralocorticoid component	
	therapy		
	No abnormal lab/pituitary MRI scan		
	but symptoms persist:		
	Repeat labs in 1 to 3 weeks/MRI in		
	1 month		
	Suspicion of adrenal crisis (for Delay or discontinue avelumab therapy		
example, severe dehydration,	Rule out sepsis		
potension, shock out of Stress dose of i.v. steroids with mineralocorticoid activity			
proportion to current illness)	I.V. fluids		
	Consult endocrinologist		
	If adrenal crisis ruled out, then treat as above for symptomatic		
	endocrinopathy		

ADL: activities of daily living; ALT: alanine aminotransferase; AST: aspartate aminotransferase; CT: computerized tomography; irAE: immune-related adverse event; i.v.: intravenous; LFT: liver function test; LLN: lower limit of normal; MRI: magnetic resonance imaging; NCI-CTCAE: National Cancer Institute-Common Terminology Criteria for Adverse Event; NSAIDs: nonsteroidal anti-inflammatory drugs; T4: free thyroxine; TSH: thyroid-stimulating hormone; ULN: upper limit of normal.

4.3.2 Management of Infusion-Related Reactions

Treatment Modification for Symptoms of Infusion-Related Reactions Caused by Avelumab

NCI-CTCAE Grade	Treatment Modification for Avelumab
Grade 1 – mild Mild transient reaction; infusion interruption not indicated; intervention not indicated	Decrease the avelumab infusion rate by 50% and monitor closely for any worsening

	The total infusion time for avelumab should not exceed120 minutes
Grade 2 – moderate	Stop avelumab infusion
Therapy or infusion interruption indicated but responds	
promptly to symptomatic treatment (for example,	Resume infusion at 50% of previous rate once infusion-
antihistamines, NSAIDs, narcotics, i.v. fluids);	related reaction has resolved or decreased to at least
prophylactic medications indicated for \leq 24 h	Grade 1 in severity, and monitor closely for any
	worsening
Grade 3 or Grade 4 – severe or life-threatening	Stop the avelumab infusion immediately and disconnect
 Grade 3: Prolonged (for example, not rapidly 	infusion tubing from the subject
responsive to symptomatic medication and/or	
brief interruption of infusion); recurrence of	Subjects have to be withdrawn immediately from
symptoms following initial improvement;	avelumab treatment and must not receive any further
hospitalization indicated for clinical sequelae	avelumab treatment
 Grade 4: Life-threatening consequences; 	
urgent intervention indicated	

i.v.: intravenous; NCI-CTCAE: National Cancer Institute-Common Terminology Criteria for Adverse Event; NSAIDs: nonsteroidal anti-inflammatory drugs.

Once the avelumab infusion rate has been decreased by 50% or interrupted due to an infusion-related reaction, it must remain decreased for all subsequent infusions. If the subject has a second infusion-related reaction Grade ≥ 2 on the slower infusion rate, the infusion should be stopped and the subject should be removed from avelumab treatment. If a subject experiences a Grade 3 or 4 infusion-related reaction at any time, the subject must discontinue avelumab. If an infusion reaction occurs, all details about drug preparation and infusion must be recorded.

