chloride solution into the infusion bag. Gently invert the mixture 10 times. Infusion bags must not be shaken, in order to avoid foaming or excessive shearing of the protein solution. The preparation must be carefully inspected as it should result in a homogeneous looking clear solution, free of visible particles.

For detailed information on the assigned dose levels and the concrete volumes to be replaced to prepare the target doses, please refer to the clinical trial protocol or to the manual of preparation.

Storage and stability:

Avelumab drug product must be stored at 2°C to 8°C until use. The storage condition is based on data from ongoing long term stability studies with avelumab.

Avelumab drug product stored at room (23°C to 27°C) or higher temperatures for extended periods of time might be subject to degradation. Avelumab drug product must not be frozen. Rough shaking of the solution must be avoided.

For application in clinical trials, avelumab drug product must be diluted with 0.45% or 0.9% saline solution (sodium chloride injection) supplied in an infusion bag. The chemical and physical in-use stability for the infusion solution of avelumab in 0.45% or 0.9% saline solution has been demonstrated for a total of 24 hours at room temperature. However, from a microbiological point of view, the diluted solution should be used immediately and is not intended to be stored unless dilution has taken place in controlled and validated aseptic conditions. If not used immediately, in-use storage times and conditions prior to administration are the responsibility of the user.

No other drugs should be added to the solution for infusion containing avelumab.

Route of administration for this study: Intravenous infusion over 1 hour.

Side effects:

For the purpose of regulatory reporting requirements during clinical development, the following AEs will be considered as expected and met the threshold of casual association (based on comprehensive evaluation) defined by the Sponsor:

- Infusion-related reactions including hypersensitivity reactions

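### Section 4.3.2 leaves two infusion-reaction sequences unreconciled: a Grade 1 reaction in an infusion started at the reduced rate, and a Grade 2 reaction on the slower rate after an earlier Grade 1

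*Combined protocol and SAP*

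**What the plan says.** Section 4.2.1 states that avelumab "will be administered as a 60 minute intravenous (IV) infusion every 2 weeks", and Section 8.1 agrees: "Intravenous infusion over 1 hour".

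The table in Section 4.3.2 gives an action by grade:

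- Grade 1: "Decrease the avelumab infusion rate by 50% and monitor closely for any worsening". The same row carries the limit: "The total infusion time for avelumab should not exceed120 minutes".
- Grade 2: stop the infusion, then, once the reaction has settled sufficiently, "Resume infusion at 50% of previous rate". The time limit is not repeated in this row.
- Grade 3 or 4: stop at once and withdraw from avelumab.

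Neither the Grade 1 nor the Grade 2 row is limited to a first reaction. The paragraph below the table adds two rules. Once the rate has been cut, "it must remain decreased for all subsequent infusions". And: "If the subject has a second infusion-related reaction Grade ≥ 2 on the slower infusion rate, the infusion should be stopped", with removal from avelumab as the consequence. The same paragraph requires full recording of how the drug was prepared and infused whenever a reaction occurs.

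**The concern.** A patient who has already reacted once is the patient for whom bedside staff most need a single instruction. In two situations Section 4.3.2 does not give one.

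In the first, a mild reaction in an already slowed infusion calls for a further slowing that the time limit in the same row does not allow. In the second, a moderate reaction after an earlier mild one leads either to resuming more slowly or to permanent removal, depending on how one phrase is read.

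The trial runs at seven sites. If they resolve these situations differently, comparable patients will be managed differently, and the count of patients who stop for adverse events, one of the tolerability measures in Section 9.5, will depend partly on how each site read the section.

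**Working it through.** **Inputs.** Full-rate infusion time: 60 minutes (4.2.1, 8.1). Rate factor at a Grade 1 or 2 reaction: 0.5 (4.3.2 table). Cap: 120 minutes (4.3.2, Grade 1 row). Reduced rate carried forward (4.3.2 text). Pauses are counted as zero, which favours staying within the cap.

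**1. The plan's own figure.** A whole infusion at half rate takes 60/0.5 = 120 minutes. The cap is therefore the length of an infusion run entirely at half rate.

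**2. First cut, at minute t of a 60-minute infusion.** Total = t + 2(60 - t) = 120 - t, always within the cap. At t = 30 the total is 90 minutes.

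**3. Further cut in a later infusion already started at half rate, at minute t.** Total = t + 2(120 - t) = 240 - t, which is above 120 for every t below 120:

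- t = 30: 210 minutes
- t = 60: 180 minutes
- t = 108 (90% of the dose given): 132 minutes

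So a Grade 1 reaction at any point in such an infusion puts the cut and the cap in conflict. This holds whether the first reaction was Grade 1 or Grade 2.

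**4. Two cuts within the same infusion.** Let f1 and f2 be the shares of the dose given at the first and second cut. Total = 60·f1 + 120(f2 - f1) + 240(1 - f2) = 240 - 60·f1 - 120·f2. This is within 120 minutes when f1 + 2·f2 ≥ 2.

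- f1 = 0.5, f2 = 0.8: 30 + 36 + 48 = 114 minutes, within the cap.
- f1 = 0.25, f2 = 0.5: 15 + 30 + 120 = 165 minutes, above it.

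A second cut in the same infusion may therefore fit or not, depending on timing.

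**5. The sequences side by side.**

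| Sequence | Table | Text below table | Result |
|---|---|---|---|
| Any first cut, then Grade 1 in a later infusion | Halve again, stay within 120 minutes | Removal not triggered (needs Grade ≥ 2) | Cannot be carried out as written |
| Grade 1, then Grade 2 on the slower rate | Stop, resume at half the previous rate | Removal on one reading, not on the other | Open |
| Grade 2, then Grade ≥ 2 on the slower rate | Resume if Grade 2, withdraw if Grade 3-4 | Removal on either reading | Settled by the specific text |
| Any Grade 3 or 4 | Withdraw | Withdraw | Consistent |

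The two readings in the second line come from the phrase in "If the subject has a second infusion-related reaction Grade ≥ 2 on the slower infusion rate, the infusion should be stopped". It can mean a second reaction, whatever the first was, that is now Grade 2 or higher; that patient is removed. Or it can mean the second of the reactions that were themselves Grade 2 or higher; that patient has had only one, so the table applies. On the latter reading, resuming in a later infusion again gives at least 240 - t minutes, and the section does not say whether the cap covers the Grade 2 row.

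**6. Size.** Section 1.6 reports infusion-related reactions in 134 of 717 patients (18.7%), all grades. Applied to 39 patients, 0.187 × 39 = 7.3 with a first reaction. The documents give no recurrence rate. If 10% to 30% of these react again on the slower rate (an assumption), that is 0.7 to 2.2 patients. This is a loose upper figure, because it also counts the sequences that the section handles consistently.

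**The case against.** Several points on the other side have force.

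- *The cap as a floor on slowing.* Because 120 minutes is exactly 60/0.5, the limit can be read as meaning that the rate never goes below half. On that reading there is no clash, only an unstated order of precedence. This is plausible, but the row gives the cut and the limit together and ranks neither, so a site has to supply the ranking itself.
- *Specific over general.* The paragraph below the table addresses reactions on the slower rate, so it can fairly be taken to override the rows. That makes the second sequence an ambiguity rather than a certain contradiction. It does not remove the ambiguity, which lies in the overriding sentence itself.
- *The Pharmacy Manual.* Section 4.2.1 refers to it for administration instructions, and it is not among the documents. It may settle the matter in practice, so divergence between sites is a possibility and not an established fact. Sections 4.2.2 and 4.4 nevertheless send sites to Section 4.3, and to 4.3.2 in particular, for managing these reactions.
- *Frequency.* Section 4.4 makes premedication mandatory, and Section 1.6 does not say whether the pooled cohort had it. The number affected may be smaller than the figure above.

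A reader might also infer more than the documents support. It is not true that the rules fail at every second reaction, or that a further cut always breaks the cap; steps 4 and 5 show the exceptions. The same-infusion exception is itself limited, since the Grade 3 definition includes symptoms that recur after initial improvement, and such a reaction leads to withdrawal. Nor would a partly delivered dose go undocumented, because Section 4.3.2 already requires the infusion details to be recorded.

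**Conclusion.** The point holds for two sequences only. In an infusion started at the reduced rate, a Grade 1 reaction triggers a cut that gives 240 - t minutes and cannot meet the 120-minute limit in the same row. For Grade 2 on the slower rate after an earlier Grade 1, table and text give opposite actions on one fair reading. The first rests on the 60-minute infusion time and on taking the Grade 1 row at its word for repeat reactions; the second rests on the wording alone.

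Few patients are likely to be affected, and the 0.7 to 2.2 figure depends on an assumed recurrence rate. The consequence for each is substantial, since one reading ends treatment for good and the other continues it. The point bears on patient safety, on exposure, and on the count of adverse-event discontinuations in Section 9.5. A reader might infer that it could tip the final decision between 8 and 9 responders. Nothing in the documents shows such a link, and the sample size is unaffected. It is an inconsistency in a safety instruction that should be corrected; it is not a flaw in the design.

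**What to change.** The sponsor should reconcile the table, the 120-minute limit and the paragraph below the table for the two sequences, and state which instruction prevails in each:

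1. A Grade 1 reaction in an infusion already started at the reduced rate: whether the further cut or the time limit governs.
2. A Grade 2 reaction on the slower rate after an earlier Grade 1: whether the Grade 2 row or the removal sentence governs, with the removal sentence reworded so that it has one meaning.

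It would help to say at the same place whether the limit also covers the Grade 2 row and whether a pause counts toward infusion time. The Pharmacy Manual should be checked for agreement. Which clinical rule applies is for the sponsor to decide; none is proposed here.

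The cost is a few lines in Section 4.3.2. No new case report form field is needed, because the section already requires the infusion details to be recorded.

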4.3.3 Severe Hypersensitivity Reactions and Flu-Like Symptoms

If hypersensitivity reaction occurs, the subject must be treated according to the best available medical practice. A complete guideline for the emergency treatment of anaphylactic reactions according to the Working Group of the Resuscitation Council (United Kingdom) can be found at https://www.resus.org.uk/pages/reaction.pdf. Subjects should be instructed to report any delayed reactions to the investigator immediately.

A. Symptoms

- Impaired airway
- Decreased oxygen saturation (< 92%)
- Confusion
- Lethargy
- Hypotension
- Pale/clammy skin
- Cyanosis

B. Management

- Epinephrine injection and dexamethasone infusion
- Subject should be placed on monitor immediately
- Alert intensive care unit for possible transfer if required

For prophylaxis of flu-like symptoms, 25 mg of indomethacin or comparable nonsteroidal antiinflammatory drug (NSAID) dose (for example, ibuprofen 600 mg, naproxen sodium 500 mg) may be administered 2 hours before and 8 hours after the start of each dose of avelumab i.v. infusion. Alternative treatments for fever (for example, paracetamol) may be given to subjects at the discretion of the investigator.

